5 DOSING DELAYS

Subjects should be assessed clinically for toxicity at each visit using the NCI CTCAE v4.03 grading scale (https://evs.nci.nih.gov/ftp1/CTCAE/CTCAE_4.03_2010-06-14_QuickReference_5x7.pdf).

Dosing will occur only if a subject's clinical assessment is acceptable as determined by the Principal Investigator and/or Treating Neurologist. Subjects should be advised to seek immediate medical help and inform their Principal Investigator and/or Treating Neurologist if they experience signs or symptoms of an infection including a respiratory infection or meningoencephalitis.

A minimum of 16 weeks should be observed between subsequent infusions. If the postponement of an infusion visit occurs which subsequently results in less than 16 weeks before the next infusion visit, the case should be escalated to the Sponsor for consideration.

5.1 CRITERIA FOR ONGOING TREATMENT

Repeat treatment of ublituximab/oral placebo or teriflunomide/IV placebo should be administered per protocol provided that:

- Renal function is continually assessed
- Liver enzyme levels are monitored monthly for the first 6 months
- Recovered from Grade 3-4 non-hematologic toxicity to Grade 2 or less.
- Subject remains compliant to taking teriflunomide or oral placebo and all study scheduled study assessments.
- Treatment may be delayed to recover from toxicity, such as Infusion Related Reaction or per the discretion of the PI and/or Treating Neurologist.

5.2 GUIDANCE FOR SUSPECTED RELAPSE

If a subject experiences a suspected relapse at any study visit after the 1st dose of either study medication, the following actions are to be taken:

Suspected Relapse	Action to be Taken
At Scheduled Infusion Visit	Perform an unscheduled relapse visit and do not perform the infusion visit. The scheduled infusion visit is postponed until a) treatment of relapse has been completed, and b) subject is neurologically stable, per PI/Treating Neurologist discretion
At Non-Infusion Visit	Perform the unscheduled relapse visit and skip the scheduled non-infusion visit. Most of the assessments that should be performed at the scheduled non-infusion visits are also performed at the unscheduled relapse visit, so the scheduled non-infusion visit can be completely skipped and marked as Not Done in the CRF. However, the following assessments should still be done: -Subject diary and teriflunomide/oral placebo administration

Suspected Relapse	Action to be Taken
	- MRI will still be done (ideally prior to steroid treatment/ if not, then after 30 days)
At Early Withdrawal From Treatment Visit	Perform the unscheduled relapse visit and skip the scheduled non-infusion visit. The patient should then return for the Early Withdrawal from Treatment Visit once a) treatment of relapse has been completed, and b) subject is neurologically stable, per PT/Treating Neurologist discretion.
Teriflunomide/Oral Placebo	Administration of teriflunomide/oral placebo can continue during a relapse at discretion of the PI/Treating Neurologist

5.3 GUIDANCE FOR LABORATORY ABNORMALITIES

For RMS subjects, the hematologic dose modifications are graded by the CTCAE v4.03 (https://evs.nci.nih.gov/ftp1/CTCAE/CTCAE_4.03_2010-06-14_QuickReference_5x7.pdf).

If a subject experiences neutropenia, thrombocytopenia, anemia, and elevated liver enzymes at any study visit after the 1st dose of either study medication, the following actions are to be taken:

Worst CTCAE Grade Toxicity	Action to be Taken
Neutropenia	
Grade	Management
≤ Grade 1	No action required.
Grade 2	No action required.
Grade 3 or 4 1st and Subsequent Occurrences	
Withhold study medications (both ublituximab/oral placebo and teriflunomide/IV placebo). If during an infusion visit, postpone entire infusion visit. If during a non-infusion visit, entire visit can be conducted. MRI can proceed as scheduled.
 
Repeat hematology testing within 2 weeks. For confirmed neutropenia Grade 3 or 4, repeat hematology testing at the discretion of the PI and/or Treating Neurologist until <Grade 3.
 
Resume teriflunomide/oral placebo at discretion of PI and/or Treating Neurologist if < Grade 3.
 
Perform the next ublituximab/IV placebo infusion at discretion of PI and/or Treating Neurologist if < Grade 3.

Management of neutropenia are per institution guidelines and if in the opinion of PI and/or Treating Neurologist, are appropriate for subject care.	

Worst CTCAE Grade Toxicity	Action to be Taken
Thrombocytopenia or Anemia	
Grade	Management
≤ Grade 1	No action required.
Grade 2	No action required.

Worst CTCAE Grade Toxicity	Action to be Taken
Thrombocytopenia or Anemia	
Grade	Management
Grade 3 or 4 1st and Subsequent Occurrences	
Withhold study medications (both ublituximab/oral placebo and teriflunomide/IV placebo). If during an infusion visit, postpone entire infusion visit. If during a non-infusion visit, entire visit can be conducted. MRI can proceed as scheduled.
 
Repeat hematology testing within 2 weeks. For confirmed thrombocytopenia or anemia Grade 3 or 4, repeat hematology testing at the discretion of the PI and/or Treating Neurologist until <Grade 3.
 
Resume teriflunomide/oral placebo at discretion of PI and/or Treating Neurologist if < Grade 3.
 
Perform the next ublituximab/IV placebo infusion at discretion of PI and/or Treating Neurologist if < Grade 3.

Management of thrombocytopenia and anemia are per institution guidelines and if in the opinion of PI and/or Treating Neurologist, are appropriate for subject care.	

Worst CTCAE Grade Toxicity	Action to be Taken
Elevated Liver Enzymes (ALT and AST)	
Grade	Management
≤ Grade 1	No action required.
Grade 2, 3 or 4 1st and subsequent occurrences	
Withhold study medications (both ublituximab/oral placebo and teriflunomide/IV placebo). If during an infusion visit, postpone entire infusion visit. If during a non-infusion visit, entire visit can be conducted. MRI can proceed as scheduled.
 
Repeat chemistry testing within 2 weeks. For confirmed liver enzyme(s) Grade 2 or higher, repeat chemistry weekly until <Grade 2.
 
Resume teriflunomide/oral placebo at discretion of PI and/or Treating Neurologist if < Grade 2.
 
Perform the next ublituximab/IV placebo infusion at discretion of PI and/or Treating Neurologist if < Grade 2.

Management of elevated liver enzymes are at the discretion of the PI and/or Treating Neurologist and should be discussed with CRO.	

6 SCHEDULE OF ASSESSMENTS AND PROCEDURES

Individual trial procedures are detailed in Tables 5-7. It may be necessary to perform these procedures at unscheduled time points if deemed clinically necessary by the Treating and Examining Neurologists.

Additional evaluations/testing may be deemed necessary by the Treating Neurologist and/or the Sponsor for reasons related to subject safety.

Table 5: Schedule of Assessments and Procedures: Screening through Week 20

	Screening	Baseline		Treatment Period							Unscheduled Relapse Visit ¹⁴	
	Week		W1	W1	W2	W3	W4	W8 ⁴	W12 ⁴	W16 ⁴	W20 ⁴	
	Day ⁴	D (-28 to 0)	D1	D2	D8	D15	D28	D56 ⁴	D84 ⁴	D112 ⁴	D140 ⁴	
Subject consent	X											X ¹⁰
Medical history	X											
Serum pregnancy test ¹	X ¹¹											X
Urine pregnancy test ^{1,5}					X	X	X	X	X	X	X	
EDSS, MSFC, and neurological examination ^{4,13}	X	X ²²							X			X ¹⁸
Physical examination ⁸ & vital signs (heart rate, blood pressure, temperature and body weight) ^{4,13}	X	X	X	X	X	X	X	X	X	X	X	X
MSQoL ⁵⁴ (inclusive of SF36), SDMT, and FIS assessment ¹³		X										
MRI ^{4,13}	X								X			
Subject diary and teriflunomide or oral placebo dispensation		X							X			
12 lead ECG ⁹	X	X			X							
Blood collection for CBC, pancreatic enzymes and serum chemistry ^{3,4,20}	X	X	X	X	X	X	X	X	X	X	X	X
Urinalysis ¹³	X	X	X	X	X	X	X	X	X	X	X	X
Blood collection for B lymphocyte cell counts (% CD19+ B cells) ^{3,4}	X	X	X	X	X	X	X	X	X	X	X	X
Fibrinogen ^{3,4}		X			X							X
Teriflunomide drug concentration test		X ^{3,17}										
Subject diary review and teriflunomide/oral placebo accountability		X	X	X	X	X	X	X	X	X	X	X
Serology: HIV, HCV, HBV, varicella ²	X											
Anti-Drug Abs (ADA) ^{3,7}		X			X							
PT/INR ⁵		X										
Quantitative immunoglobulin ^{3,4,13}		X			X							X
Adverse events (CTCAE v4.03)		X	X	X	X	X	X	X	X	X	X	X
Concomitant medication	X	X	X	X	X	X	X	X	X	X	X	X
Ublituximab/placebo infusion ²⁴		X			X							
Initiate teriflunomide/oral placebo administration ¹⁶		X										

Table 6: Schedule of Assessments and Procedures: Weeks 24 through 84

Week	Treatment Period						Unscheduled Relapse Visit ¹⁴
	W24 ⁴	W36 ⁴	W48 ⁴	W60 ⁴	W72 ⁴	W84 ⁴	
	Day ⁴	D168 ⁴	D252 ⁴	D336 ⁴	D420 ⁴	D504 ⁴	
Subject consent							X ¹⁰
Urine pregnancy test ^{1,5,21}	X	X	X	X	X	X	
Serum pregnancy test ¹							X
EDSS, MSFC and neurological examination ^{4,13}	X	X	X	X	X	X	X ¹⁸
Physical examination ⁸ & vital signs (heart rate, blood pressure, temperature and body weight) ^{4,13}	X	X	X	X	X	X	X
MSQoL54 (inclusive of SF36), SDMT and FIS assessment ^{5,13}	X		X				
MRI ^{4,13}	X		X				
Subject diary and teriflunomide or oral placebo dispensation	X	X	X	X	X	X	
12 Lead ECG ⁹	X		X		X		
Blood collection for CBC, pancreatic enzymes and serum chemistry ^{3,4,12}	X	X	X	X	X	X	X
Urinalysis ¹³	X	X	X	X	X	X	X
Blood collection for B lymphocyte cell counts (% CD19+ B cells) ^{3,4}	X	X	X	X	X	X	X
Fibrinogen ^{3,4}	X		X		X		X
Teriflunomide drug concentration test			X ³				
Study diary review and teriflunomide/oral placebo accountability	X	X	X	X	X	X	X
Anti-Drug Abs (ADA) ^{3,7}	X		X		X		
Quantitative immunoglobulin ^{3,4}	X		X		X		X
Adverse events (CTCAE v4.03)	X	X	X	X	X	X	X
Concomitant medication	X	X	X	X	X	X	X
Ublituximab/placebo infusion ²⁴	X		X		X		

Table 7: Schedule of Assessments and Procedures: End of Study, Follow-up, and Early Withdrawal from Treatment Visits

	End of Study		Follow-up Period				Early Withdrawal from Treatment	Unscheduled Relapse Visit ¹⁴
Week	W96 ⁴	W100 ⁴	W104 ⁴	W108 ⁴	W112 ⁴	W116 ⁴		
Day ⁴	D672 ⁴	D700 ⁴	D728 ⁴	D756 ⁴	D784 ⁴	D812 ⁴		
Subject consent							X	X ¹⁰
Serum pregnancy test ¹							X	X
Urine pregnancy test ^{1,5}	X	X	X	X	X	X		
EDSS, MSFC and neurological examinations ⁴	X						X	X ¹⁸
Physical examination ⁸ & vital signs (heart rate, blood pressure, temperature and body weight) ⁴	X	X	X			X	X	X
Subject Phone Consult				X	X			
MSQoL54 (inclusive of SF36), SDMT and FIS assessment ⁵	X						X	
MRI	X ⁴						X ⁴	
12 lead ECG							X	
Blood collection for CBC, pancreatic enzymes and serum chemistry ⁴	X	X	X				X	X
Urinalysis	X	X	X				X	X
Blood collection for B lymphocyte cell counts (% CD19+ B cells) ⁴	X	X	X				X	X
Fibrinogen							X	X
Anti-Drug Abs (ADA)^{3,7}								
Quantitative immunoglobulin ⁴	X						X	X
Adverse events (CTCAE v4.03)	X	X	X	X	X	X	X	X
Dispensation of activated charcoal or cholestyramine for accelerated procedure and dispensation of rapid elimination diary		X					X ²³	
Completion of accelerated teriflunomide elimination procedure; elimination procedure diary review and elimination drug accountability ¹⁹			X					
Teriflunomide drug concentration test	X ¹²					X	X ¹²	

Concomitant medication	X	X	X	X	X	X	X	X
Study diary review and teriflunomide/oral placebo accountability¹⁴	X						X	X

¹ For women of child bearing potential

² To confirm negative HIV 1 and 2, Hepatitis B Virus, Hepatitis C Virus and varicella

³ Labs drawn pre-infusion on any infusion days

⁴ Weeks 8 and beyond, collections/assessments may occur ± 5 days from specified time points, except for MRI scans, which can occur ± 7 days on Weeks 12 and 96 and must be performed pre-infusion on infusion days (- 7 days) on Weeks 24 and 48. MRI scan at Early Withdrawal from Treatment Visit should be performed within 4 weeks after withdrawing from the study.

⁵ Prior to each infusion except PT/INR which is completed at baseline. Urine Pregnancy Test on non-infusion days subjects will test upon arrival at the site

⁶ Prior to infusion and 30 minutes +/- 15 minutes post-infusion on infusion days. For non-infusion days, one PK sample should be obtained

⁷ Anti-Drug Antibodies are antibodies developed against ublituximab

⁸ Physical examination will occur on all visits except Week 1 Day 2 and Week 2 Day 8

⁹ Within 2 hours pre-infusion and 60 minutes +/- 15 minutes post-infusion on any infusion day

¹⁰ Re-consent following a suspected relapse is required if the relapse is confirmed by IRAP or by the Treating Neurologist (Treating Neurologist medically confirmed relapse), whichever comes first. Re-consent must occur within 6 weeks after first reporting of relapse. Re-consent may occur at the next schedule office visit but may require an unscheduled visit if the relapse occurs between Weeks 24 and 96 (where the frequency of scheduled visits is every 12 weeks).

¹¹ Serum pregnancy test must be completed within 5 days prior to Week 1 Day 1

¹² Obtain blood sample for teriflunomide drug concentration test prior to first dose of accelerated teriflunomide elimination procedure

¹³ Prior to each infusion

¹⁴ The Unscheduled Relapse Visit will be conducted if a possible relapse is reported by the subject. The visit is to be planned as soon as possible, within 7 days from subject notification of the relapse to the site. Infusion visit is delayed until relapse is back to baseline, or Treating Neurologist/PI does not expect any improvements.

¹⁶ Teriflunomide/oral placebo administration shall be taken in the morning until the last day of Week 95. Alternative dosing times are allowed if necessary.

¹⁷ Sample for teriflunomide concentration to be collected before the first oral dose of teriflunomide/oral placebo

¹⁸ For Unscheduled Relapse Visit, EDSS assessment (by Examining Neurologist) and neurological examination (by Treating Neurologist) will be performed independently

¹⁹ Acknowledge completion of 11-day accelerated teriflunomide elimination procedure started at week 100

²⁰ If the subject experiences neutropenia, thrombocytopenia, anemia, or elevated liver enzymes, follow guidelines and procedures on laboratory retests and study treatment per Section 5.2.

²¹ Post Week 24 (including during the Follow-Up Period), urine pregnancy test will be administered every 4 weeks (+/- 5 days). On days when there is not a study visit, the subject will need to perform the test at home and contact the study site to provide the outcome

²² Week 1/Day 1 EDSS must be assessed within 1 day prior to randomization (i.e., on the day before randomization or on the day of randomization but before randomization occurs)

²³ Start 11-day accelerated teriflunomide elimination procedure the day after the early withdraw from treatment visit is completed

²⁴ Pre-medicate 30-60 minutes prior to each infusion of ublituximab/IV placebo with an anti-histamine (diphenhydramine 50 mg or equivalent) and corticosteroid (dexamethasone 10-20 mg or equivalent)

6.1 OVERVIEW

All subjects should visit the study center on the days specified within this protocol. The complete schedule of assessments is shown in Section 6 (Tables 5, 6, and 7) and Appendix F. The screening physical examination with vital signs, medical history, evaluation of concomitant medications, EDSS (fatigue will not contribute to the EDSS score), complete blood count/full blood count (3 part differential accepted), serum chemistry, and a baseline ECG should be done within 28 days prior to initiation of treatment. For women of child bearing potential, a serum pregnancy test should be completed within 5 days prior to Week 1 Day 1. MRI scans should be performed ≤ 28 days prior to initiation of treatment.

Week 1/Day 1 EDSS must be assessed within 1 day prior to randomization (i.e., on the day before randomization or on the day of randomization but before randomization occurs) and must be documented.

6.2 LABORATORY EVALUATION

1. Hematologic profile: CBC/FBC with differential and platelet count should be obtained at:
 - a. For all subjects:
 - i. Blood collection for CBC at screening, and Week 1 Day 1 (pre-dose), Day 2, Day 8, Week 3 Day 15 (pre-dose), and Weeks 4, 8, 12, 16, 20, 24 (pre-dose), 36, 48 (pre-dose) 60, 72 (pre-dose), 84, 96, 100 and 104
 - b. For subjects who have an Unscheduled Relapse Visit, blood collection for CBC and serum chemistry will be assessed
 - c. For subjects who withdraw from treatment early, blood collection for CBC and serum chemistry will be assessed
 - d. Hematology and differential panel will include the following: hemoglobin, hematocrit, red blood cell count, mean corpuscular hemoglobin, white blood cell count, neutrophils, lymphocytes, monocytes, eosinophils, basophils, and platelets
2. Serum chemistry should be obtained at screening, and Week 1 Day 1 (pre-dose), Day 2, Day 8, Week 3 Day 15 (pre-dose), and Weeks 4, 8, 12, 16, 20, 24 (pre-dose), 36, 48 (pre-dose) 60, 72 (pre-dose), 84, 96, 100 and 104. The serum chemistry parameters to be analyzed are shown in the table below.

Serum Chemistry		
Albumin	Glucose	SGPT [ALT]
Alkaline phosphatase	LDH	Sodium
Bicarbonate	Magnesium	Total bilirubin
BUN	Phosphate	Total Protein
Calcium	Potassium	Uric acid
Chloride	SGGT	Indirect/direct bilirubin
Creatinine	SGOT [AST]	

3. Serum pregnancy test should be obtained within 5 days prior to the initiation of therapy and at Week 104 for women of childbearing potential. Additionally, serum pregnancy test will be

obtained if a female subject of childbearing potential withdraws from treatment early or has an Unscheduled Relapse Visit. Serum pregnancy test may be performed at any time during the study in case of a missed or late menstrual cycle.

4. Urine pregnancy test will be performed on a monthly basis, inclusive of the 20 week Follow-up Period. During study visits urine pregnancy tests will be performed at the site and on days of ublituximab or IV placebo infusion urine pregnancy tests will be performed prior to infusion. Post Week 24, urine pregnancy test will be administered every 4 weeks (+/- 5 days), unless serum testing is conducted instead. On days when there is not a study visit, the subject will need to perform at home and provide the outcome to the study staff at the study site. If a urine pregnancy test is positive, the subject should be informed of the potential teratogenic effects, therefore consideration to withhold further teriflunomide/oral placebo dosing should be made and a follow-up appointment should be scheduled as soon as possible where a serum pregnant test will be performed for confirmation.
5. PT/INR should be drawn on Week 1 Day 1 prior to study medications administration. This is the only time PT/INR will be drawn.
6. Quantitative immunoglobulin (IgG, IgM, IgA) test should be analyzed on Week 1 Day 1 (pre-dose) and Week 3 Day 15 (pre-dose), Weeks 24 (pre-dose), 48 (pre-dose), 72 (pre-dose) and 96. Additionally, quantitative immunoglobulin (IgG, IgM, IgA) test will be analyzed for subjects who withdraw from treatment early or have an Unscheduled Relapse Visit.
7. Fibrinogen tests
 - a. All subjects will have 5 serum samples taken prior to the infusions on Week 1 Day 1, Week 3 Day 15 and Weeks 24, 48, and 72. Additionally, fibrinogen will be analyzed for subjects who withdraw from treatment early or have an Unscheduled Relapse Visit.
8. Anti-Drug Antibody (antibodies developed against ublituximab; Central Lab)
 - a. All subjects will have 6 serum samples taken to assess for the presence of ADA prior to the infusions on Week 1 Day 1, Week 3 Day 15 and Weeks 24, 48, and 72. In addition, a serum sample will be taken at Week 96.

[REDACTED]

- a. Serum samples will be drawn from all subjects pre-infusion any time on infusion days of ublituximab or IV placebo and at 30 minutes +/- 15 minutes post infusion on infusion days (Week 1 Day 1, Week 3 Day 15, Weeks 24, 48, and 72). One additional serum sample will be taken on Week 96.

[REDACTED]

[REDACTED]

[figure not shown]
[REDACTED]

[REDACTED]

10. Plasma concentration for teriflunomide

- a. In order to assess teriflunomide compliance, four plasma samples will be taken from all subjects. The first sample will be taken prior to oral administration of teriflunomide or oral placebo on Week 1 Day 1. The second sample will be taken prior to infusion of ublituximab or IV placebo on Week 48. The third sample will be taken at Week 96, prior to first dose of accelerated teriflunomide elimination procedure which begins at Week 100. The last plasma sample for teriflunomide will be taken at Week 116 following the accelerated teriflunomide elimination procedure with either active charcoal or cholestyramine. For subjects who withdraw from treatment early, a blood sample will be collected at the Early Withdrawal from Treatment Visit prior to first dose of accelerated teriflunomide elimination procedure.
 - b. Only plasma samples from subjects treated with teriflunomide will be analyzed for plasma teriflunomide concentrations. See the Laboratory Manual for PK collection and processing instructions.
11. Liver function panel: SGOT/AST, SGPT/ALT, serum gamma-glutamyl transferase (SGGT), total bilirubin, direct/indirect bilirubin. Samples will be taken for analysis as directed in the schedule of assessment (Tables 5, 6, and 7) and as shown in bullet number 2 (Serum Chemistry)
12. Pancreatic enzyme panel: serum amylase and lipase. Samples will be taken for analysis as directed in the schedule of assessment (Tables 5, 6, and 7) and as shown in bullet number 2 (Serum Chemistry)
13. Urinalysis panel for routine safety will be sampled as follows at screening, and Week 1 Day 1 (pre-dose), Day 2, Day 8, Week 3 Day 15 (pre-dose), and Weeks 4, 8, 12, 16, 20, 24 (pre-dose), 36, 48 (pre-dose) 60, 72 (pre-dose), 84, 96, 100 and 104. The urine is to be analyzed for the following pH, ketones, protein, glucose, blood, urobilinogen, bilirubin, microscopic sediment, specific gravity and leucocyte esterase. Additionally, a sample should be obtained for subjects who withdraw from treatment early or have an Unscheduled Relapse Visit.
14. B lymphocyte cell counts (% CD19+ B cells). Samples will be taken for analysis at screening, and Week 1 Day 1 (pre-dose), Day 2, Day 8, Week 3 Day 15 (pre-dose), and Weeks 4, 8, 12, 16, 20, 24 (pre-dose), 36, 48 (pre-dose) 60, 72 (pre-dose), 84, 96, 100 and 104. Additionally, B lymphocyte cell counts will be analyzed for subjects who withdraw from treatment early or have an Unscheduled Relapse Visit.
15. At screening the following assessments will be performed: HIV, HCV, HBV, Varicella

Note, the study site staff will remain blinded to the results of the PK, ADA and teriflunomide concentration analysis for all subjects. The study site staff will also remain blinded to the results of the B lymphocyte cell counts (% CD19+ B cells) from Week 1 Day 1 onwards.

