6.10 END OF STUDY FOLLOW-UP

After early termination of trial or at the end of study visit at Week 96, subjects will enter a 20-week Follow-up Period inclusive of the accelerated elimination of teriflunomide. The 11-day elimination procedure will commence at Week 100 for all subjects who completed all study visits including Week 96. For those subjects who had terminated early (discontinued or withdrawn from the study), the 11-day elimination procedure will commence the day after the Early Withdrawal from Treatment Visit. The follow up period will include visits at Weeks 100, 104, and 116. Weeks 108 and 112 will be performed via a phone call.

For subjects who withdraw their consent to participate in the study, the site should inform these subjects of the 20-week Follow-up Period inclusive of the accelerated teriflunomide elimination procedure and document this in the eCRF. Participation in the 20-week Follow-up Period inclusive of the accelerated teriflunomide elimination procedure for subjects who withdraw early is left to the discretion of the subject. If he/she elects not to participate in the 20-week Follow-up inclusive of the accelerated teriflunomide elimination procedure, after withdrawing consent and after discussion with the site, it should be documented in the eCRF.

For subjects who will participate in the 20-week Follow-up Period inclusive of the accelerated teriflunomide elimination procedure after withdrawing consent for this study, a new consent form to participate in the 20-week Follow-up Period inclusive of the accelerated teriflunomide elimination procedure will need to be signed. If he/she re-consents, the sites will complete the eCRF for Weeks 100, 104, 108, 112, and 116, accordingly.

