8.9.6 ANTI-DRUG ANTIBODY (ADA) ANALYSIS

Immunogenicity results will be reported based on all subjects in the safety population. The percentage of subjects developing ADA will be summarized. .

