Time Required: | Full day; *Approximately 3 – 5 hours plus time for MRI*

Treatment: | Initiate the teriflunomide rapid elimination process (11 days) via activated charcoal or cholestyramine

Tests: | Serum Pregnancy Test; *must be negative results*
 MRI
 12 lead ECG

Clinical Assessments: | Adverse Event
 Concomitant medications
 EDSS, MSFC, MSQOL54, SDMT, FIS and neurological examination
 Physical examination/vital signs

Labs: | Hematologic profile; *CBC/FBC with differential and platelet count*
 Serum chemistry panel;

Labs:
 (see Laboratory Manual for full details, instructions, and shipping information)

Serum Chemistry		
Albumin	Glucose	SGPT [ALT]
Alkaline phosphatase	LDH	Sodium
Bicarbonate	Magnesium	Total bilirubin
BUN	Phosphorus	Total Protein
Calcium	Potassium	Uric acid
Chloride	SGGT	Indirect/direct bilirubin
Creatinine	SGOT [AST]	

Pancreatic Enzyme
 Absolute B cell lymphocyte count and % B cell
 Urinalysis
 Fibrinogen
 Teriflunomide Drug Concentration Test
 Quantitative Immunoglobulin

Documents / Forms: | Informed Consent Form
 eCRF documentation
 AE and SAE Reporting (If applicable)
 Sample shipping
 Subject diary review and teriflunomide or oral placebo accountability

Drug Preparation / Dispensation: | None

**Timing and
Sequence
Considerations:**

Once signed consent is obtained, procedures can be scheduled for the day at Investigator and subject convenience.

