#### **2.4.8 Analyses of Anti-Drug Antibody (ADA)**

Immunogenicity to determine the absence or presence of ADA will be done for only the subjects randomized to ublituximab. Immunogenicity results, specifically the impact of ADA on the PK of ublituximab, will be reported in conjunction with the population PK analysis. . The percentage of

subjects developing ADA will be summarized by actual treatment group. A listing will be provided for ADA data.

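### No ADA sample is scheduled after the last infusion for ublituximab subjects who leave treatment early, so ADA that first appears after that infusion goes undetected

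*Protocol*

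**What the plan says.** The ADA schedule is in Protocol 6.2 item 8: "All subjects will have 6 serum samples taken to assess for the presence of ADA prior to the infusions" at Week 1 Day 1, Week 3 Day 15 and Weeks 24, 48 and 72. It continues: "In addition, a serum sample will be taken at Week 96". The ADA entry in the protocol synopsis gives the same six time points.

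Other tests in Protocol 6.2 have an explicit draw for people who stop early. For fibrinogen, item 7 says: "Additionally, fibrinogen will be analyzed for subjects who withdraw from treatment early or have an Unscheduled Relapse Visit". Items 1, 6, 10, 13 and 14 make a similar provision for CBC and chemistry, immunoglobulins, teriflunomide concentration, urinalysis and B cells. Item 8 makes none. The Appendix F laboratory list for Early Withdrawal from Treatment includes, for example, the "Teriflunomide Drug Concentration Test", but not ADA. After early termination, Protocol 6.10 says: "The follow up period will include visits at Weeks 100, 104, and 116". Its procedure lists for those visits contain no ADA sample.

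On analysis, Protocol 8.9.6 says: "Immunogenicity results will be reported based on all subjects in the safety population". It then asks for the share of subjects who develop ADA. SAP 2.2.1 also places ADA on the Safety Population. SAP 2.4.8 says the determination "will be done for only the subjects randomized to ublituximab" and summarises by actual treatment. SAP 2.5.1 has a general rule that leaves people with missing values out of percentages for categorical variables, unless something else is specified.

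**The concern.** ADA incidence is one of the safety endpoints named in the protocol synopsis. Every planned sample before Week 96 is taken just before an infusion, so it can only show the response to earlier infusions. The response to a given infusion is seen at the next infusion visit or at Week 96. Someone who leaves treatment reaches neither, and the visit that replaces them has no ADA tube although blood is drawn there for several other tests.

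Antibodies that first appear after a leaver's last infusion are then never observed. If that person is counted as negative, the reported percentage is too low. What is at stake is a descriptive safety figure for one arm. No hypothesis test depends on it.

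**Working it through.** **Count of samples.** Five pre-infusion draws plus one at Week 96 give 5 + 1 = 6, which reproduces the figure in item 8. None is left over for Early Withdrawal.

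**What a leaver has.** Study days are those in Protocol Tables 5 to 7. Each row is a subject who stops after the infusion shown and before the next planned ADA draw.

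| Last infusion | Samples after first dose | Samples after last infusion | Days to next planned ADA draw |
|---|---|---|---|
| Week 1 Day 1 | 0 | 0 | 15 − 1 = 14 |
| Week 3 Day 15 | 1 | 0 | 168 − 15 = 153 |
| Week 24 | 2 | 0 | 336 − 168 = 168 |
| Week 48 | 3 | 0 | 504 − 336 = 168 |
| Week 72 | 4 | 0 | 672 − 504 = 168 |

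The single post-dose sample in the second row is the one drawn on Day 15 before the infusion. It reflects the first dose only.

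**Who counts as negative.** A leaver with at least one post-dose sample, all of them negative, counts as negative under any reading. For a leaver with only the pre-dose Day 1 sample, the texts pull apart. Protocol 8.9.6 keeps all Safety Population subjects, while the SAP 2.5.1 rule could drop this person as missing.

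**Size.** Let d be the share of ublituximab subjects who leave early, p the true ADA incidence (taken as equal in leavers and stayers), and f the share of leavers' ADA that appears only after the last infusion. If all leavers stay in the denominator:

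reported = p − d × p × f, so understatement = d × p × f.

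For d, I use the 10% dropout allowance in the worked example of Protocol 8.8 and SAP 1.3.1 (219 × 1.10 = 240.9, given there as 241). With about 220 ublituximab subjects (synopsis, Study Design), 0.10 × 220 = 22 leavers. The documents give neither p nor f, so both are assumptions.

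| Understatement at d = 10% (percentage points) | f = 0.25 | f = 0.5 | f = 1 |
|---|---|---|---|
| p = 10% | 0.25 | 0.5 | 1.0 |
| p = 30% | 0.75 | 1.5 | 3.0 |
| p = 60% | 1.5 | 3.0 | 6.0 |

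For example, 0.10 × 0.10 × 0.25 = 0.0025, or 0.25 points.

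The absolute ceiling is reached if every leaver developed ADA only after the last infusion and was counted negative: 22/220 = 10.0 points. It is 11/220 = 5.0 points at 5% dropout and 44/220 = 20.0 points at 20%.

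**The case against.** The strongest reply is that the missing tube is real but its consequences are easily exaggerated. Several stronger readings are tempting, and the documents do not support them.

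- **That early leavers are untested or all count as negative.** Leavers with two or more infusions have one to four post-dose samples. A positive result in any of these would be counted. Only ADA that first arises after the last infusion is lost.
- **That no early leaver can have a later sample.** SAP 2.4.2 allows subjects off drug to keep attending visits, so one could be sampled at Week 96. A pre-infusion sample could also be drawn and the infusion then not given. However, Protocol 3.3 and 6.10 send people who stop to the 20-week follow-up, where no ADA is listed.
- **That first-infusion-only leavers certainly count in the percentage.** SAP 2.5.1 may exclude them. The denominator is unsettled, and an ADA-evaluable set could lie in blacked-out text (SAP 2.2.5 is redacted).
- **That the shortfall is large.** With 10% leaving, 10% ADA in stayers and 30% in leavers, the true rate is 0.9 × 10% + 0.1 × 30% = 12.0%, against 9.0% reported. That is a worst case: it credits no leaver's ADA as detected and uses an assumed leaver rate.
- **That leavers are enriched for ADA because they stop after infusion reactions.** Protocol 7.5.2.4 says such a reaction is not grounds for discontinuation. Nothing in the documents ties withdrawal to ADA.
- **That Table 7 proves the omission.** Its ADA row, as it can be read, is blank even at Week 96, where the text requires a sample. It cannot serve as evidence.
- **That the protocol and SAP disagree on arms, so the percentage is diluted.** Assaying ublituximab subjects and summarising by actual treatment keeps the arms apart.

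These replies remove the larger claims. They do not supply a sample after the last infusion for a leaver who enters follow-up.

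**Conclusion.** The sampling gap stands on Protocol 6.2 item 8, the Appendix F Early Withdrawal list and the follow-up visit lists. It can lower the reported ADA percentage, but only through antibodies that first appear after the last infusion in leavers who are counted as negative. At 10% dropout and an assumed 10% incidence, that is about 0.25 to 1.0 percentage points for f between 25% and 100%. It grows in proportion to incidence and dropout. The calculation assumes that the dropout allowance approximates early treatment withdrawal, that leavers and stayers have equal incidence, and that all leavers stay in the denominator. If first-infusion-only leavers are dropped as missing, they no longer count as negatives, but their ADA status stays unknown. This is a minor point about a descriptive safety summary, worth acting on because the remedy is cheap.

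**What to change.** 1. Add an ADA tube to the Early Withdrawal from Treatment blood draw in Protocol 6.2 item 8, Table 7 and Appendix F. In the same edit, reconcile the blank Week 96 cell in the Table 7 ADA row with the text.
2. In SAP 2.4.8, define the denominator as ublituximab-treated subjects with at least one ADA sample after the first dose, and align Protocol 8.9.6 with it. Report the number with no sample after their last infusion.

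The cost is one tube in an existing draw and one assay per early leaver (about 22 at the 10% allowance), plus a short SAP addition. The added sample detects only ADA already present at that visit and helps only for leavers who attend it. The count of subjects without a later sample is therefore needed as well. If sampling can no longer be changed, the SAP part can still be done on its own.
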